- **Waiver of Informed Consent**. The trial is pragmatic in nature, assessing the impact of implementation strategies (i.e. *Nudge* vs. *Nudge+*) delivered to PCPs through minor adjustments to existing workflow delivered through the EHR. Changes to workflow are by necessity systematically applied to all PCPs within the practices. Further, these changes to workflow are being implemented as part of leadership commitment to deploying the *SAFE Firearm* program and EHR Nudges and Facilitation with data collection to allow for evaluation (i.e., *SAFE Firearm* will be considered standard of practice). Because PCPs will still be free to engage with parents as they see fit and the implementation strategies represent minimal risk to PCPs and parents, we have requested a **waiver of informed consent** for allowing EHR/Administrative data to be collected for Aims 1 and 3. This approach will also aid implementation integrity and generalizability by avoiding behavior changes related to observation (i.e., the Hawthorne effect). The PI has worked closely with the Nudge Unit in the past on similar pragmatic trials that have received this waiver of informed consent, and our study team has designed the study with their trials in mind. As such, we believe there are several reasons to justify why a waiver of informed consent is requested (and has been granted for similar studies at Penn). First, it is not feasible to consent every provider and parent. Second, if consent was obtained from providers and parents, they would know they were being studied and this could change their behavior. This could potentially disrupt the design of the study and make interpretation of the findings challenging. Third, clinicians are not forced to implement the *SAFE Firearm* program (which, as a reminder, is an evidence-based practice that is being implemented in both health systems) and parents are not forced to engage in a conversation with their provider and they are not forced to take a cable lock. In all aims, providers can choose to use their best clinical judgement when it comes to the *SAFE Firearm* program. This research involves no more than minimal risk to the participants and will not adversely impact the rights and welfare of participants. As described above, the waiver is essential to research as this research could not be practicably carried out without this waiver.
- **Waiver of Documentation of Consent for Online/Mailed/Phone Surveys**. All surveys completed by parents (Aims 1 and 3) and PCPs (Aims 1 and 2) will be completed via phone, mail, or electronic platforms, and thus we are requesting waiver of written documentation of consent from the IRB. The required elements of informed consent will be described to the participant and, if they agree to participate, participants will consent by agreeing and proceeding to the electronic/phone survey. Mailed survey participants will be instructed to review

the consent form before completing the survey. Only participants who agree will be able to proceed to the online/phone survey. Mailed survey participants will be instructed not to complete the survey until they have reviewed the consent form and decide to participate. For phone surveys, the required elements of consent will be described to the potential participant at the beginning of the survey, before any research questions are asked. If the participant verbally agrees to be complete the survey, the research staff who is conducting the interview will document the consent process. This research activity presents no more than minimal risk of harm to subjects and involves no procedures for which written consent is normally required outside of the research context.

- **Partial Waiver of Consent for Part 1 Parent Survey.** For the one-question Part 1 parent survey, we will share a link to the consent form in the introductory message sent before the survey question text message or in the survey invitation sent via email or patient portal message. All the required elements of consent will be described to the participant. In the informed consent form, they will be instructed to review the consent form before completing the survey. The consent form will also indicate that their completion of the survey indicates their consent to participate in the research. This research activity presents no more than minimal risk of harm to subjects and involves no procedures for which written consent is normally required outside of the research context.
- **Waiver of Documentation of Consent for Interviews.** All interviews will be completed remotely and audio-recorded. The required elements of consent will be described to the potential participant at the beginning of the interview, before any research questions are asked. If the interview participant verbally agrees to be interviewed, the research staff who is conducting the interview will document the consent process. This research activity presents no more than minimal risk of harm to subjects and involves no procedures for which written consent is normally required outside of the research context.
- For the equity supplement, we also request a **waiver of written documentation of informed consent** (as described above) for the qualitative interview since the research presents no more than minimal risk of harm to subjects and involves no procedures for which written consent is normally required outside of the research context. The required elements of informed consent will be described over the phone or videoconference before any study activities occur.

RESOURCES NECESSARY FOR HUMAN RESEARCH PROTECTION:

Adequate facilities are available at Penn, HFHS, and KPCO. The members of the research team are outlined in the application and include the PI, research investigators, full time research staff, and part time undergraduate research assistants. The entire team will be overseen by the PI. All personnel will complete required training before being granted access to any identifying information. This includes training on confidentiality through the CITI course. All Penn personnel will also sign confidentiality statements. These confidentiality statements will specify the procedures for reporting unintentional breaches in confidentiality to the PI. The confidentiality statements also specify that violations of participants' confidentiality, either unintentional or deliberate, may result in termination of hire. The PI will conduct training with all research personnel regarding data, limits of confidentiality, maintaining confidentiality, and proper study procedures. Personnel from HFHS and KPCO sign similar confidentiality statements and undergo similar research training within their respective systems.

REFERENCES

Statistical Analysis Plan (SAP)
Adolescent and child Suicide Prevention In Routine clinical Encounters (ASPIRE) study

Official Title: A comparative effectiveness trial of strategies to implement firearm safety promotion as a universal suicide prevention strategy in pediatric primary care

Funding Agency: National Institute of Mental Health (NIMH)

NIH Grant Number: R01 MH123491

University of Pennsylvania Protocol Number: 844327

Principal Investigator: [name]

ClinicalTrials.gov Number: NCT04844021

Original SAP: 09 August 2021

Final SAP: 03 July 2023

Table of Contents

Final Statistical Analysis Plan	2
SAP amendments	4
Original Statistical Analysis Plan	6
Study blinding details	7

Final Statistical Analysis Plan

Date of approval by study team: 03 July 2023 (Prior to unblinding and data analyses; primary outcome data analyses commenced on 25 July 2023)

ASPIRE Statistical Analysis Plan for Primary Comparison of Nudge vs Nudge+

Primary outcome: Reach, defined as the composite (multiplicative) of two binary outcomes:

- 1) discussion of safe firearm storage (Yes/No)
- 2) offered a cable lock (Yes/No)

Therefore, the primary outcome will be coded as a 1 (successful program delivery) if both components were documented as “Yes” in the EHR; otherwise, the primary outcome will take value 0. The primary outcome is measured at the patient-visit level. If the same patient has multiple visits data from each visit will be included in the analysis. If multiple children in the same family, all visits for all children will be included.

As a secondary analysis, we will analyze 1) and 2) individually. We hypothesize that the analysis of component 2 (cable lock offers) will provide results similar to the results for the composite Reach outcome since fewer clinicians will endorse the cable lock than discussion and it is rare for clinicians to offer the lock without also doing the discussion.

Missingness in the primary outcome: Due to the nature of the EHR systems at the two sites, there is a non-negligible amount of missingness in the two binary outcomes that make up the composite Reach variable. More specifically, there is a large amount of missingness in the “offered a cable lock” outcome at one site, since clinicians were able to exit the EHR smartlist after documenting the first outcome about safe storage discussion.

Unfortunately, missingness in one of the two outcomes induces missingness in the composite Reach outcome. In the primary analysis, we will treat any missing value as a “No.” As a result, there will be no missing values in the Reach outcome for the primary analysis.

Statistical analysis plan:

Here, we describe the statistical analysis plan for the primary analysis of Reach.

Check balance across arms:

We will first calculate standardized mean differences (SMD) of both individual-level (sex, race, etc.) and clinic-level (size, presence of stakeholder, etc.) variables. Variables with a SMD greater than 0.2 will be included as covariates in the outcome models. The SMD for a given variable will be calculated as:

$$SMD = \frac{\bar{Y}_2 - \bar{Y}_1}{\hat{\sigma}_{Pooled}}$$

where \bar{Y}_2 is the sample average of Nudge+ cluster means; \bar{Y}_1 is the sample average of Nudge cluster means; and $\hat{\sigma}_{Pooled}$ is the standard deviation of all N=30 cluster means.

Primary outcome model:

Missing values in the Reach outcome will be imputed as having not delivered the S.A.F.E. Firearm program. Given the definition of Reach will be completely observed (no missingness), we plan to model the patient-level binary Reach outcome using a logistic generalized estimating equation (GEE) with an exchangeable correlation at the clinic level. This model provides an estimate of the marginal effect of Nudge+ versus Nudge, i.e., the expected difference in the population if all clinics had received Nudge+ compared to giving all clinics Nudge only. In addition to the clinic-level indicator of randomized treatment assignment (corresponding to the parameter of interest), we will include the following set of covariates: sex (patient-level), health system (clinic-level), clinic size measured by number of well-child visits in the year prior to the trial launch (clinic-level), and clinician partner status (clinic-

level). We chose to include patient-level sex based on pilot findings that the rate of program delivery differs significantly for male versus female patients and by patient race. The three clinic-level covariates will be included because they were used in the covariate constrained randomization and are therefore anticipated to be highly related to Reach.

Because of the moderately small number of clinics in the trial, we will apply the Kauermann and Carroll small cluster correction to avoid underestimation of variance (e.g., using EMPIRICAL=ROOT statement with PROC GLIMMIX in SAS). Furthermore, if effort and availability of reliable software allow, we will use a custom nested exchangeable correlation instead of an exchangeable correlation clustering at the clinic level. The nested exchangeable structure will contain two parameters: one for a common correlation within clinician and the other for the correlation between different clinicians practicing at the same clinic. If available, the nested exchangeable correlation structure be more efficient if it more closely resembles the true correlation structure in the data.

Hypothesis testing:

We have proposed to use a three-sided hypothesis test using a Type I error of 0.05 to simultaneously test whether 1) Nudge+ and Nudge are equivalently effective, and 2) Nudge+ is superior to Nudge. This hypothesis testing framework required our statistical team to elicit an equivalence margin from the study investigators. To prioritize interpretability and actionability of our main study findings, we elicited the margin on the marginal probability scale. We determined that a margin of 10 percentage points would be reasonable to declare the two interventions equivalent. In other words, if we determine with statistical confidence that the rate of Reach in Nudge+ is more than 10 percentage points higher than the rate in Nudge, then Nudge+ will be deemed superior. A three-sided testing framework allows us to test equivalence, inferiority, and superiority without adjusting the Type I error for multiple tests. To implement this framework and perform these tests on the marginal probability scale, we will construct a series of Wald tests for the risk difference along a grid of null parameter values. The risk difference and its standard error (SE) will be obtained using PROC GLIMMIX's MARGINS statement. The SE will reflect the small cluster correction to the degrees of freedom (DF) by the EMPIRICAL statement (we will check that that the degrees of freedom match). For a given null value, μ_s , we will compute the t-statistic:

$$t_s = \frac{EST - \mu_s}{SE}$$

where EST denotes the estimated risk difference. We will compare this t-statistic to the critical value of the t-distribution with appropriate DF to obtain a p-value and reject the null hypothesis that the risk difference is equal to μ_s . We will repeat this process for a fine grid of μ_s values, $s \in \{1, \dots, S\}$, and form a confidence interval for the true risk difference. If the confidence interval is completely contained within the equivalence margin, Nudge and Nudge+ will be concluded to be equivalently effective. If the lower limit of the confidence interval is greater than the upper limit of the equivalence margin, Nudge+ will be deemed superior to Nudge.

SAP amendments

1. Details were added to further operationalize the analysis plan from what was originally specified in the study's protocol paper ([name] et al., 2021).
2. The primary outcome of the study was changed from parent-reported receipt of *S.A.F.E. Firearm* (i.e., fidelity) to clinician-reported delivery of *S.A.F.E. Firearm* in the electronic health record (i.e., reach).
 - o Both the study's National Institute of Mental Health Program Officer and Data Safety and Monitoring Board approved of this change on 02 March 2022, ahead of the trial's launch on 14 March 2022.
 - o A detailed description of the rationale for this change is below as submitted to funding agency, National Institute of Mental Health.

Summary. Insights from behavioral economics, or how individuals' decisions and behaviors are shaped by finite cognitive resources (e.g., time, attention) and mental heuristics, have been underused in efforts to increase the use of evidence-based practices in implementation science. Using the example of firearm safety promotion in pediatric primary care, which addresses an evidence-to-practice gap in universal suicide prevention, we aim to determine: is a less costly and more scalable behavioral economic-informed implementation strategy (i.e., "Nudge") powerful enough to change clinician behavior or is a more intensive and expensive facilitation strategy needed to overcome implementation barriers? The Adolescent and child Suicide Prevention in Routine clinical Encounters (ASPIRE) hybrid type III effectiveness-implementation trial uses a longitudinal cluster randomized design. We will test the comparative effectiveness of two implementation strategies to support clinicians' use of an evidence-based firearm safety practice, *S.A.F.E. Firearm*, in 32 pediatric practices across two health systems. All pediatric practices in the two health systems will receive *S.A.F.E. Firearm* materials, including training and cable locks. Half of the practices ($k = 16$) will be randomized to receive Nudge; the other half ($k = 16$) will be randomized to receive Nudge plus 1 year of facilitation to target additional practice and clinician implementation barriers (Nudge+). The primary implementation outcome is parent-reported clinician fidelity to the *S.A.F.E. Firearm* program. Secondary implementation outcomes include reach and cost. To understand how the implementation strategies work, the primary mechanism to be tested is practice adaptive reserve, a self-report practice-level measure that includes relationship infrastructure, facilitative leadership, sense-making, teamwork, work environment, and culture of learning. The ASPIRE trial will integrate implementation science and behavioral economic approaches to advance our understanding of methods for implementing evidence-based firearm safety promotion practices in pediatric primary care. The study answers a question at the heart of many practice change efforts: which strategies are sufficient to support change, and why? Results of the trial will offer valuable insights into how best to implement evidence-based practices that address sensitive health matters in pediatric primary care.

Description of problem. Parental response to our brief survey, the method through which we collect our primary implementation outcome of fidelity, has been lower than anticipated in the pilot and pre-implementation period. Our health system partners report that overall survey response in the health systems is much lower across all projects since COVID-19. The major methodological threats of a low response rate include: (a) concerns about representativeness; (b) lower power; and (c) the need to impute missing data for most of the sample. Given these concerns, our DSMB methodologist, [name], recommended that we switch our primary outcome to reach as measured by physician electronic medical record documentation.

Steps taken. We began piloting the parent survey in May 2021 to maximize parental response rate. Our initial plan, as proposed in the grant submission, was to engage in a combination of email, text message, and mailed letters (i.e., methods found to be effective in previous work in these health systems). From May 2021 to February 2022, we conducted 13 pilots to maximize response rate, systematically changing how we approached collecting this data to ascertain the most effective approach (e.g., changing the order of outreach methods; adding messaging through patient portals, adding phone calls). Using a range of approaches, we obtained a 23% response rate, with a strong signal that phone calls are the most effective manner to obtain parental responses.

Given our desire to keep fidelity as our primary outcome, we tried two additional approaches to increase response rate. First, we piloted sending a one-question survey via email and/or text to reduce the friction and time commitment associated with responding. This resulted in a 10% response rate and is likely due to common carriers blocking text

messages that include ‘firearm,’ even though we tried many strategies to circumvent these blocks. Furthermore, it resulted in loss of valuable data since only 1 question could be asked.

Second, we tried an intensive outreach approach that included 2+ phone calls to a smaller subset of randomly selected patients (n = 100) per health system every 2 weeks. This approach allowed us to reach a 37% response rate, which is the highest response rate we have been able to obtain.

The intensive outreach approach is the most effective one. Unfortunately, the sites are not resourced from a staff perspective to engage in this approach. Making phone-calls to 100 parents every 2 weeks per site requires hundreds of phone calls and places substantial strain on our health system partners with their current staffing model. We have explored budget reallocations but we will not be able to reallocate sufficient additional resources to the sites to support the additional staff needed for this resource intensive approach, given initial budgetary cuts and unanticipated increases to the cost of gun locks due to supply chain issues.

Proposed change. We propose to change the primary outcome in the ASPIRE trial from fidelity, measured via parental report, to reach, measured via physician documentation in the EHR. Our health systems have built integrated templates in the electronic medical record for the physicians as part of the trial that enable seamless documentation and efficient data extraction. We will continue to collect fidelity as a secondary outcome from a subset of participants.

Advantages of this approach. First, we will have a complete dataset with no missing data, thus strengthening the rigor of our conclusions. Second, while we acknowledge reach will likely be an overestimate of what is occurring, the bias will impact the two arms in the same way (see table below). Third, we will still collect fidelity from a subset of participants. Our partners are currently calculating the number of patients per two weeks that they can outreach to using the intensive outreach approach. We will work with our biostatistician, [name], to potentially adjust for misclassification bias in our reach estimates by using the smaller, gold-standard validation sample of fidelity data.

Comparison of reach and fidelity (October 21-Feb 22)		
	EHR – Reach	Survey – Fidelity
Counseling	56.3%	47.9%
Locks	46.4%	31.8%
Both	45.3%	30.0%

Original Statistical Analysis Plan

Date of approval by study team: 09 August 2021 (Prior to trial launch on 14 March 2022)

The original statistical analysis plan is described in the study's protocol paper:

[name], [name], [name], et al. Study protocol for a type III hybrid effectiveness-implementation trial of strategies to implement firearm safety promotion as a universal suicide prevention strategy in pediatric primary care. *Implement Sci* 2021;16.

Study blinding details

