- *University of Pennsylvania (Penn)*. The project team at Penn will provide scientific and administrative oversight of the proposed project and all project-related activities coordinated by the investigative teams at each site. They will lead the training in facilitation at both sites and provide ongoing support to facilitators at each site. The Penn site will oversee the data analysis and interpretation of findings.
- *Northwestern University (NU)*: The project team at NU will support the Penn site at providing scientific and administrative oversight of the proposed project and all project-related activities coordinated by the investigative teams at HFH and KPCO. They will also lead some quantitative and qualitative data collection (e.g., implementation clinician survey; clinician, point people, and leader qualitative interviews), management, and analysis. They will provide ongoing support as needed across all sites.
- *Henry Ford Health (HFH)*. The project team at HFH will oversee the following activities at the participating clinics within their health system: the dissemination of *SAFE Firearm* program materials to clinics, brief clinician training, the build of the Epic SmartLists, and facilitation provided to clinics randomized to the *Nudge+* condition. They will also coordinate the collection of quantitative data from parent and clinician participants and ensure safe data storage using REDCap.
- *Kaiser Permanente Colorado (KPCO)*. The project team at KPCO will oversee the following activities at the participating clinics within their health system: the dissemination of *SAFE Firearm* program materials to clinics, brief clinician training, the build of the Epic SmartLists, and facilitation provided to clinics randomized to the *Nudge+* condition. They will also coordinate the collection of quantitative data from parent participants and ensure safe data storage using KPCO's REDCap. They will coordinate with Penn and Northwestern University for quantitative data collection (surveys) from PCPs which will be stored in Penn's REDCap and qualitative (interview) data collection from PCPs and health system leaders.

5. Subject Follow-up:

If it is decided that we will follow-up with participants, we will submit a modification and outline our reconsenting plan as necessary.

STUDY PROCEDURES:

1. Detailed Description:

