- *Nudge+*. Clinics randomized to the *Nudge+* implementation strategy will receive the *Nudge* implementation strategy (as described above) as well as facilitation. Facilitation is external support delivered by health system employees not employed within the clinic site. It will be offered for 12 months to each clinic, in keeping with other implementation trials. We will use a train-the-trainer model to train facilitators at HFH and KPCO to ensure they achieve facilitator core competencies with an eye toward implementation of *SAFE Firearm*. This may also involve sending key facilitators to a training around how to successfully implement facilitation. The role of the facilitator is to engage with study clinics, to assist each clinic in setting change and performance goals around the implementation of *SAFE Firearm*, and to troubleshoot implementation barriers. Our approach to facilitation was informed by established facilitation manuals (i.e., Veteran Health Affairs QUERI facilitation manual and AHRQ practice facilitation manual) and includes six stages. First, facilitators will engage in a pre-implementation readiness assessment for each clinic to identify potential implementation barriers and to develop relationships with stakeholders. Second, facilitators will hold kick-off meetings that signal the formal launch of the implementation strategy activities that include identifying where in the workflow *SAFE Firearm* can be implemented. This includes when *SAFE Firearm* will be delivered during the well-child visit, who in the clinic will be responsible for storing the cable locks, where the locks will be stored, and other workflow-related matters. Third, in the first 3 months of the active implementation period, facilitators will work with clinics around goal setting and metrics related to *SAFE Firearm*. During this period, the facilitator will conduct onsite/virtual visits to engage with practice leadership and PCPs once a month. In this phase, facilitators will also start to develop a sustainment plan in collaboration with stakeholders. Fourth, in months 3-9, the facilitators will engage in active implementation efforts based upon barriers assessed in the pre-implementation readiness phase as well as barriers that emerge as PCPs and clinics begin implementing. This includes established implementation strategies such as Plan-Do-Study-Act cycles and audit and feedback. All activities will be tracked via established logs to ensure the ability to understand which strategies are delivered and for implementation fidelity purposes. Fifth, in months 9-12, facilitators will engage in continued efforts to maintain gains and begin to enact the sustainment plan developed in the kick-off meeting. Sixth, in month 12, facilitation activities will complete and the clinics will transition to the formal maintenance period. Throughout the course of the active implementation period, facilitators will offer expert consultation (i.e., 2 webinars and technical assistance via email and phone as needed); and regular peer-to-peer calls supported by facilitators where clinics can share their experience.

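### The SAP's premise that EHR over-reporting is equal in both arms has no by-arm evidence and is doubtful, so the primary contrast may mix delivery with documentation

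*SAP*

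**What the plan says.** The Final SAP codes a visit as reached "if both components were documented as “Yes” in the EHR; otherwise, the primary outcome will take value 0". Under Missingness in the primary outcome it treats any missing entry as No. It explains that at one site clinicians could leave the SmartList before reaching the cable-lock item.

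This outcome replaced parent-reported fidelity. The rationale given to the funder, under Advantages of this approach in SAP amendments, accepts that EHR reach is likely too high and then says "the bias will impact the two arms in the same way (see table below". The table is titled "Comparison of reach and fidelity (October 21-Feb 22". The same section says the outcome change was approved "ahead of the trial's launch on 14 March 2022". As mitigation, the rationale says the team will work with its biostatistician to "potentially adjust for misclassification bias in our reach estimates by using the smaller, gold-standard validation sample of fidelity data".

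In the Protocol (Study Procedures, Detailed Description), Nudge clinics receive the SmartList only. In Nudge+ the facilitator is also to "assist each clinic in setting change and performance goals around the implementation of" SAFE Firearm, and works with clinics on metrics in the first three months. Of months 3 to 9 the Protocol says: "This includes established implementation strategies such as Plan-Do-Study-Act cycles and audit and feedback".

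Under Hypothesis testing, the SAP judges the risk difference against a margin of 10 percentage points.

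**The concern.** The outcome is what the clinician records, and the arms differ in a way that could change recording as well as care. There are two routes.

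- **False Yes.** Clinicians who are set goals and audited may record Yes more readily for the same encounter.
- **Completeness.** A blank lock item counts as No. Coaching that only gets clinicians to finish the SmartList raises reach with no change for the family.

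The trial asks whether facilitation improves delivery, and the decision rests on an absolute risk difference. If documentation differs by arm, that difference is partly a documentation effect. If error is equal, the risk difference is still pulled toward zero. The rationale for changing the outcome sets the first possibility aside on evidence that cannot address it, and the Final SAP has no analysis to separate the two effects.

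**Working it through.** **1. What the table shows.** It gives percentages without counts or arms, so there is no sample-size or power figure to reproduce.

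| | EHR | Parent | Gap (points) |
|---|---|---|---|
| Counseling | 56.3% | 47.9% | 8.4 |
| Lock | 46.4% | 31.8% | 14.6 |
| Both | 45.3% | 30.0% | 15.3 |

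It is internally consistent: Both does not exceed the smaller component in either column (45.3 ≤ 46.4; 30.0 ≤ 31.8). The composite gap of 15.3 points is larger than the 10-point margin.

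**2. What it cannot show.** The data end in February 2022 and the trial launched on 14 March 2022. No visit in the table was made under a randomized strategy, so it says nothing about over-reporting in Nudge compared with Nudge+.

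**3. Model.** Let p be true delivery, Se the chance that a delivered visit is recorded Yes, and F the chance that an undelivered visit is recorded Yes. Then

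observed reach = Se × p + F × (1 − p).

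Inputs: p = 0.30 and observed reach = 0.453, both from the table. Assumptions: the two columns refer to the same visits, parent report is the truth, and Se is 0.9 to 1.0. The documents do not give Se.

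F = (0.453 − Se × 0.30) / 0.70
- Se = 1.0: F = 0.153 / 0.70 = 0.219
- Se = 0.9: F = 0.183 / 0.70 = 0.261

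**4. Equal error in both arms.** Subtracting one arm from the other gives observed RD = (Se − F) × true RD.
- Se = 1.0: factor 0.781, so a true 10 points appears as 7.8
- Se = 0.9: factor 0.639, so a true 10 points appears as 6.4

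Counting missing as No could push Se lower. At Se = 0.8, F = 0.304, the factor is 0.496 and 10 points appears as 5.0. A true difference of zero stays zero.

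**5. Unequal false-Yes rate, no true difference.** Spurious RD = (extra F in Nudge+) × 0.70.
- Extra 0.05 gives 3.5 points
- Extra 0.10 gives 7.0 points
- Extra 0.143 gives 10.0 points. At Se = 1.0 this is F = 0.36 in Nudge+ against 0.22 in Nudge

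**6. Unequal completeness, no true difference.** Spurious RD = (extra Se in Nudge+) × 0.30. For example, Se of 1.0 against 0.9 gives 0.10 × 0.30 = 3.0 points. The SAP calls missingness non-negligible but gives no rate, by arm or overall.

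**7. Against the decision rule.** Equivalence needs the whole interval inside the margin; superiority needs the lower limit above +10. Assume 15 clinics per arm, 48,475 / 30 ≈ 1,616 visits per clinic, reach near 0.5, a 95% interval with 25 degrees of freedom (t ≈ 2.06), no gain from covariates, and ICC 0.02 to 0.07 (0.07 is the Protocol's planning value).

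SE = √[2 × 0.25 × (ICC + (1 − ICC)/1,616) / 15] = 0.026 to 0.049, so the half-width is 5.4 to 10.0 points.

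Superiority then needs an estimate of 15.4 to 20.0 points. With no true difference and Se = 1.0, the Nudge+ false-Yes rate would have to reach 0.219 + 0.154/0.70 = 0.44, up to 0.219 + 0.200/0.70 = 0.50.

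**The case against.** A reader might infer that facilitation acts directly on the primary-outcome record, that equal bias has therefore been disproved, and that extra Yes entries could by themselves make Nudge+ superior. The documents support none of these. The Protocol never says the SmartList is the source for the facilitators' metrics or audits, and clinics also keep lock-distribution logs. Facilitation could equally make records more accurate. On the illustrative precision above, superiority with no delivery difference would need the false-Yes rate roughly to double, and nothing in the documents points to a shift of that size. Nor could an observed 10 points be called equivalent, because its interval would cross the margin.

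The numerical inputs are also soft. The documents do not say that the EHR and survey columns cover the same visits. Pilot survey response ran from 10% to 37%, so part of the 15.3-point gap may be non-response or recall. Parent report is itself imperfect evidence: at one health system the team overseeing facilitation is also the one of which the Protocol says "They will also coordinate the collection of quantitative data from parent and clinician participants", and Study blinding details does not list site staff among those blinded.

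Finally, some protection is already planned. The Protocol defines reach as clinician-reported, keeps parent-reported fidelity and lock distribution as secondary outcomes, and plans inverse probability weighting for survey non-response. The Final SAP covers the primary comparison, so its silence on secondary outcomes does not drop them.

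All of this limits the size and certainty of the point. It does not supply by-arm evidence for equal bias, and a separate analysis of fidelity is not the same as estimating recording error in each arm.

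**Conclusion.** The equal-bias premise is unverified, not refuted. The cited table cannot support it, and there is a specific reason to doubt it in the difference between the arms and the missing-as-No rule. A bias favouring Nudge+ is the more plausible direction, but it is not established.

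The step 4 and 5 figures indicate scale only; they rest on treating the columns as paired and parent report as truth. At that scale, differential documentation could block an equivalence finding or inflate a real difference, and equal error would understate one. The primary analysis remains valid for documented reach. What lacks support is reading its result as a statement about delivery on the strength of equal bias. This is a worthwhile, low-cost improvement rather than a defect that invalidates the analysis.

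**What to change.** Add one specified sensitivity analysis to the SAP, in place of an adjustment that is only potential:

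1. Link each parent fidelity response to the EHR entry for the same visit. The Protocol draws survey participants from the EHR extract, so this looks feasible.
2. Estimate sensitivity and the false-Yes rate separately by arm, with weighting for non-response and clustering by clinic. Do this for each component, and for both together where a parent answered both. Part 1 of the survey asks only one component, so the composite needs parents who also completed Part 2.
3. Report SmartList missingness by arm and site.
4. Present the Nudge+ minus Nudge risk difference, with intervals, for EHR reach, parent-reported receipt, and EHR reach corrected with arm-specific error rates.
5. Describe the primary result as documented reach, and do not rely on equal bias when interpreting it. The rationale sent to the funder can stand as a historical record.

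It would also help to state the data source of the facilitators' metrics and audits.

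The cost is SAP text and analysis of survey data the trial already plans to collect. The arm-specific error rates will be imprecise because response is low, so the corrected difference should inform interpretation, not replace the primary result. The SAP dates the start of primary analyses as 25 July 2023; if this analysis is added after that, it should be dated and labelled accordingly.
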